5.5.2 Secondary Endpoints

The secondary efficacy endpoint is the proportion of subjects with clinical success defined as a score of clear or almost clear (score of 0 or 1) on the Investigator Global Assessment (IGA) at Visit 4/Week 12 (Day 84).

Equivalent Efficacy

The compound hypothesis to be tested for clinical equivalence between test and reference is:

$$H_0 : p_T - p_R < -0.20 \text{ or } p_T - p_R > 0.20 \text{ versus}$$

$$H_A : -0.20 \leq p_T - p_R \leq 0.20.$$

Where p_T and p_R are the proportions of subjects with clinical success at Visit 4/Week 12 (Day 84) for the test and reference products, respectively. The test product will be considered to be therapeutically equivalent to the reference product if the 90% CI on the difference in their proportions of subjects with clinical success, calculated by Wald's method with Yates' continuity correction, is contained within the limits -0.20 to +0.20. Rejection of the null hypothesis supports the conclusion of therapeutic equivalence between the test and reference products for the secondary efficacy variable.

The result of the analysis in the PP population will be considered definitive and that in the mITT population as supportive.

Analysis for therapeutic equivalence will be performed based on the following SAS code (SAS Institute v.9.1.3):

P-value is chosen from Continuity Adj. Chi-Square test.

The SAS code for 90% confidence interval (trt=1 for Test, trt=2 for Reference):

```
proc freq data=XX ;
  where trt in (1,2);
  tables trt* success / alpha=0.10 riskdiff;
  output out=CIDIFF (keep= l_rdif2 u_rdif2 ) riskdiff;
run;
```

For the final 90% continuity-corrected CI, the lower limit = (l_rdif2 - yates) and the upper limit = (u_rdif2 + yates), where yates, the Yates' continuity-correction factor, is derived as

$(1/n_1+1/n_2)/2$, n_1 =number of subjects in Test arm and n_2 =number of subjects in Reference arm.

Superiority

The hypotheses to be tested for superiority of the test and reference products over Vehicle are:

$$H_0 : p_T \leq p_V \text{ versus } H_A : p_T > p_V$$

$$H_0 : p_R \leq p_V \text{ versus } H_A : p_R > p_V$$

Where p_T , p_R and p_V are the proportions of subjects with clinical success at Visit 4/Week 12 (Day 84) for the test, reference and Vehicle products, respectively. The tests will be conducted independently for the test product vs. vehicle and the reference product vs. vehicle using two-sided, $\alpha = 0.05$, continuity-corrected Z-tests. Superiority will be established if the proportion of subjects with clinical success in the active treatment group is greater than and statistically different ($p < 0.05$) from that in the Vehicle. Rejection of the null hypothesis supports the conclusion of superiority of the test and reference products over the Vehicle product for the secondary efficacy variable.

The analyses in the mITT population will be considered primary and those in the PP population as supportive.

Analysis for superiority will be performed based on the following SAS code (SAS Institute v.9.1.3):

The SAS code for p-value (trt=2 for Reference vs. trt=3 for Vehicle):

```
proc freq data=XX ;
  where trt in (2,3);
  table trt * success /chisq ;
run;
```

5.5.3 [REDACTED]

[REDACTED]

5.6 Safety Variables and Analyses

Duration of Treatment and Medication Compliance

Number of applications, days of exposure, and compliance rate will be summarized by treatment group using descriptive statistics. For each subject, the overall duration of treatment (days) will be calculated using the following formula:

(Date of last application of study medication) - (Date of first application of study medication) + 1.

Medication compliance rate (%) will be calculated for each subject as follows:

$(\text{Total number of applications used}) / (\text{Expected number of applications}) * 100\%$

Adverse Events

Adverse events (AEs) will be coded in MedDRA, version 18.1. Treatment-Emergent Adverse Event (TEAE) is defined as any AE occurs on or after application of the first dose of study drug. Number and percent of subjects reporting TEAEs will be tabulated by treatment group. Summaries will be presented by body system and preferred term for the ITT population, and further by severity and relationship to study medication. TEAEs reported by 5% or more subjects for any treatment group will also be summarized. In the summaries of incidence rates (frequencies and percentages), severity and relationship to study drug, subjects who report more than one event that are mapped to the same preferred term will be counted only once under the strongest severity and relationship, accordingly. The difference between Test and Reference treatments with regard to the severity and frequency of their dermatological adverse events will be statistically evaluated. Chi-Square or Fisher's exact test will be used to compare the proportions of subjects of the two active treatment groups who report any TEAE.

Treatment-Emergent Serious Adverse Events (TESAEs) will be discussed within the clinical study report. TEAEs, TESAEs and TEAEs that led to treatment interruption or discontinuation will be presented in data listings.

Concomitant Medications and Vitals Signs

Concomitant medications will be coded using the WHO Drug Dictionary, version September 2015, and will be presented in data listings. All vital signs data will be displayed in listings.

Erythema Severity and Application Site Reaction Assessments

Frequency and distribution of erythema severity assessment and application site reactions of dryness, burning/stinging, pruritus and scaling/peeling will be summarized and compared descriptively by visit.

Safety comparisons will be performed only for the ITT population.

6 Appendices

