**5.11 Study Medication Use, Subject Instructions and Diary**

At the baseline visit, one [REDACTED] tube of study medication from the subject kit box will be dispensed, by the third party dispenser (if possible) or designee, to enrolled subjects along with a diary card. Each subject will also receive a copy of written instructions, which detail the proper application method, and general instructions regarding the study [REDACTED]). The initial application on Day 1 will be applied by the subject and observed by study staff at the study site during the study visit to ensure subjects understand the instructions and are applying the medication appropriately. Subsequent applications of study medication should be applied as instructed starting Day 2 by the subject at home before bedtime. The study staff should instruct the subject to apply all subsequent doses of the study medication once daily before bedtime (starting on Day 2 of study treatment period) as instructed. At all subsequent study visits the study medication will be collected to assess compliance and study medication accountability. After the compliance evaluation, empty tubes will be collected and kept by the site. Tubes with remaining medication will be redispensed to the subject. In addition to the redispensed tube, the subject will receive a new tube each at Visit 2/Week 4/Day 28 ( $\pm 4$  days) and Visit 3/Week 8/Day 56 ( $\pm 4$  days).

[REDACTED] the study medication should be applied smoothly and evenly on each area of the face (chin, left cheek, right cheek, nose, forehead) and avoiding contact with the eyes (upper and lower eyelids), inside their nose/nostrils and lips [REDACTED] before bedtime (approximately the same time) once daily for 12 weeks. Subjects should be instructed to wash hands immediately after applying the study medication. Subjects should continue to use a mild cleanser to wash the face for the duration of the study. Subjects will be instructed to not use any other topical treatments or products [REDACTED] other than the study medication on their face.

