**Protocol No: PRG-NY-15-013**

treatment. An adverse event can therefore be any unfavorable and unintended sign (for example, an abnormal laboratory finding), symptom, or disease temporally associated with the use of a medicinal product, whether or not considered related to this medicinal product.

A serious adverse event (SAE) is an adverse event that results in any of the following outcomes:

- Death
- Life threatening event (i.e., the subject was, in the opinion of the investigator, at immediate risk of death from the event as it occurred. It does not include an event that, had it occurred in a more severe form, might have caused death
- Requires in subject hospitalization or prolongs hospitalization
- A persistent or significant disability/incapacity or substantial disruption of the ability to conduct normal life functions
- Congenital anomaly/birth defect
- Other adverse events that may be considered serious based upon appropriate medical judgment, may jeopardize the subject and may require medical or surgical intervention to prevent one of the outcomes listed above.

Immediately Reportable Adverse Events (IRAE): Any serious AE or any AE that necessitates discontinuation of study medication, including pregnancy.

Unexpected Adverse Event: An unexpected event is any adverse drug experience, the specificity or severity of which is not consistent with the current approved product labeling (package insert) for the study medication, the Investigator’s Brochure, or as described in the clinical protocol and consent materials.

Intensity of Adverse Events: The maximum intensity of an AE during a day should be recorded on the eCRF. If the intensity of an AE changes over a number of days, then separate entries should be made having distinct onset dates for the changes in severity.

Mild AEs are usually transient, requiring no special treatment, and do not interfere with subject’s daily activities.

Moderate AEs typically introduce a low level of inconvenience or concern to the subject and may interfere with daily activities, but are usually ameliorated by simple therapeutic measures.

Severe AEs interrupt a subject’s usual daily activity and traditionally require systemic drug therapy or other treatment.

Causal Relationship to Study Medication: The following criteria should be used in assessing the apparent causal relationship of an AE to study medication.

Definitely The AE:

- follows a reasonable temporal sequence from study medication administration

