**7.3 Eliciting and Reporting of Adverse Events**

The investigator will periodically assess subjects for the occurrence of adverse events. [REDACTED]

[REDACTED] All adverse events (as defined in Section 7.2), either observed by the Investigator or one of his/her medical collaborators, or reported by the participant spontaneously, or in response to direct questioning, will be reported and documented in the source and the study reporting forms. When reporting an adverse event, the Investigator must assign a severity grade to each event and declare an opinion on the relatedness of the event to the study medication or procedure. Serious or unexpected adverse events must be reported to Perrigo **within 24 hours** of when the Investigator first learns of the occurrence of the event.

Adverse events will be documented in the source document and recorded in a timely manner on electronic case report forms (eCRFs). Adverse events that are identified at the last assessment visit (or the early termination visit) must be recorded on the AE eCRF with the status of the AE noted.

Adverse event reporting begins from the signing of informed consent/assent. Adverse events should be followed until resolved or 30 days after the final study treatment. In any case, serious adverse events that are not resolved or considered to be chronic within 30 days of the final study treatment must be followed by the investigator until they become resolved or are considered to be

chronic (stabilized for at least 30 days). All events that are ongoing at this time will be recorded as ongoing on the eCRF.

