**9. CONSENT CONSIDERATIONS AND PROCEDURES**

It will be made clear to the subject that, for the purposes of the study, they are consenting only for topical application of medication or vehicle. Investigators may discuss the availability of the study and the possibility for entry with a potential subject without first obtaining consent/assent. However, informed consent/assent must be obtained and documented prior to initiation of any procedures that are performed solely for the purpose of determining eligibility for research, including withdrawal from current medication(s). When this is done in anticipation of, or in preparation for, the research, it is considered to be part of the research.

The study must be approved in writing by an appropriate IRB as defined by FDA regulations. A copy of the Letter of Approval from the IRB, which also contains specific identification of the documents approved, must be received by Perrigo, prior to study commencement.

Periodic status reports must be submitted to the IRB at least annually as required by the site's IRB, as well as notification of completion of the study and a final report within three months of study completion or termination. A copy of all reports submitted to the IRB must be sent to Perrigo.

The investigator(s) has both ethical and legal responsibility to ensure that each subject being considered for inclusion in this study is given a full explanation of the protocol. This shall be documented on a written informed consent/assent form, which shall be approved by the same Institutional Review Board (IRB) responsible for approval of this protocol. Each informed consent/assent form shall include the elements required by FDA regulations in 21 CFR Part 50. The

[REDACTED]

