6.1 Handling of Missing or Incomplete Dates for Adverse Events and Concomitant Medications

Adverse Events

Handling of partial dates is only considered for the start date. An adverse event with a partial start date is considered treatment emergent if:

- only the day is missing and the start month/year is the same or after the month/year of the first dose
- the day and month are missing and the start year is the same or greater than the year of the first dose date
- the start date is completely missing

Concomitant Medications

Handling of partial dates is only considered for the stop date. A medication with a partial stop date is considered concomitant if:

- only the day is missing and the stop month/year is the same or after the month/year of the first dose
- the day and month are missing and the stop year is the same or greater than the year of the first dose date
- the stop date is completely missing or the medication is ongoing

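### The SAP's treatment-emergent rules can count an AE that ended before the first dose, and do not settle how a pre-dose AE that later changes intensity is classified

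*SAP*

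**What the plan says.** **Definition.** SAP 5.6 states that a TEAE "is defined as any AE occurs on or after application of the first dose of study drug". Nothing in the definition refers to the state before treatment.

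**Incomplete dates.** For AEs, SAP 6.1 says: "Handling of partial dates is only considered for the start date". The AE is treatment-emergent in three cases: the day is missing and the start month is that of first dose or later; only the year is known and is that of first dose or later; or the start date is wholly missing. The stop date plays no part.

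**Recording.** When an AE varies in intensity from day to day, Protocol 7.2 says that "separate entries should be made having distinct onset dates for the changes in severity". This is not limited to worsening.

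**Collection period.** Protocol 7.3 says: "Adverse event reporting begins from the signing of informed consent/assent". Protocol 9 places consent before eligibility procedures, including withdrawal of current medication, and mentions a screening phase. On first dosing, Protocol 5.11 says: "The initial application on Day 1 will be applied by the subject and observed by study staff at the study site".

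**Use.** SAP 5.6 compares Test and Reference on the proportion of subjects with any TEAE, by chi-square or Fisher's exact test. Protocol 8.1.5 bases comparable safety on the proportion with any AE.

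**The concern.** AEs can be on file from before the first application. A sound TEAE rule should leave out those that ended before dosing, leave out those that only continued or improved, and keep those that got worse. The visible rules do not do this.

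For ended events, SAP 6.1 produces a wrong label even when the recorded stop date shows that the event was over before dosing.

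For events that change intensity, the outcome depends on whether the programmer applies the definition to eCRF entries or to whole events. The SAP does not say which, and neither choice is right in both directions.

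At stake is the any-TEAE proportion, one of the quantities used to judge whether Test and Reference are comparably safe. Background events added equally to both arms pull the observed difference towards zero, which favours a finding of comparability. Counting once per subject and preferred term removes duplicates only; a mislabelled entry may be the subject's sole TEAE.

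**Working it through.** The plan states no figure on this point, so there is none to reproduce. The check applies the rules as written to seven invented AE entries.

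**Inputs.** The TEAE definition (SAP 5.6), the incomplete-date rule (SAP 6.1) and the separate-entry rule (Protocol 7.2). Assumed for illustration: first application on 15 March 2016. In rows 1 to 3 one event starts on 10 March at moderate intensity; rows 2 and 3 are alternative continuations of it. The by-event column dates the whole event by its first onset.

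| # | Entry | Start | Stop | SAP, by entry | SAP, by event | With the fix |
|---|---|---|---|---|---|---|
| 1 | Pre-dose, moderate | 10 March | 18 March | no | no | no |
| 2 | Same event, now mild | 18 March | 22 March | **TEAE** | no | no |
| 3 | Same event, now severe | 18 March | 22 March | TEAE | **no** | TEAE |
| 4 | Start wholly missing | none | 12 March | **TEAE** | **TEAE** | no |
| 5 | Start day missing | March 2016 | 12 March | **TEAE** | **TEAE** | no |
| 6 | Only start year known | 2016 | 12 March | **TEAE** | **TEAE** | no |
| 7 | New after dosing | 20 March | 22 March | TEAE | TEAE | TEAE |

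Bold marks a label that the fix changes.

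**Rows 4 to 6** follow from SAP 6.1 on either reading. Each event had stopped three days before the first application. The same appendix does use the stop date to classify concomitant medications.

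**Rows 2 and 3** show the ambiguity. By entry, the improved event is counted because its new entry carries a post-dose onset date. By event, that error disappears, but the event that worsened on treatment is lost.

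On either reading four of the seven labels change. The entries were chosen to exercise the rules, so four of seven is not a rate.

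**Effect on the comparison.** Let *p* be the true any-TEAE proportion in an arm. Let *f* be the chance that a subject with no true TEAE is wrongly flagged, assumed equal in both arms. Then:

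- observed proportion = *p* + *f*(1 − *p*)
- observed difference = (1 − *f*) × (*p*_T − *p*_R)

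The difference shrinks by the fraction *f*. The documents give neither *p* nor *f*. Purely to show how the formula behaves, take true rates of 10% and 20% and *f* = 3%:

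- 0.10 + 0.03 × 0.90 = 12.7%
- 0.20 + 0.03 × 0.80 = 22.4%
- difference 9.7 points instead of 10

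This formula covers false positives only, not worsened events missed under the by-event reading.

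**The case against.** **The definition speaks of an AE, not an AE entry.** Protocol 7.2 describes one AE whose intensity changes, and the onset dates it asks for are those of the changes. Read that way, an easing pre-dose AE is not a TEAE. This stands as far as it goes: the by-entry reading is an inference, and the protocol's wording is advisory rather than mandatory. It does not rescue the definition, because the by-event reading misses worsening.

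**Pre-dose AEs may be few.** The visible schedule starts at Visit 1/Day 1, where the first application is made. If consent is given at that visit, the window is hours. A reader might infer from Protocol 9 that pre-dose AEs are to be expected. The documents show only that they are possible: the wording on medication withdrawal permits earlier consent but establishes no washout interval, and the procedures in Protocol 5.1 and 5.12.1 are partly or wholly blacked out. This stands, and limits the size of the problem.

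**Missing start dates should be rare, and counting them is conservative.** Protocol 2.2 asks for onset and end dates, and Protocol 11.1 provides edit checks and queries. That default is sensible when timing is unknown. It has no justification when a recorded stop date settles the timing.

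**A linking rule may exist out of sight.** Parts of Protocol 7.3, 7.5 and 8.1.5 and of SAP 5.2 are blacked out, and the eCRF specification is not among the documents. An event identifier may therefore already exist. The visible definition and date appendix do not use one.

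**Conclusion.** The point holds as a minor defect in two SAP rules. The incomplete-date part is the firmer: SAP 6.1 as written labels as treatment-emergent some events known to have ended before dosing. The intensity part is an unresolved ambiguity in which each available reading fails in one direction.

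The effect on the any-TEAE comparison is probably small. That judgement rests on a possibly short pre-dose window, on the rule applying alike in all arms under blinding, and on the proportional shrinkage shown above. Safety is also assessed through severity and relationship tables, a Test–Reference evaluation of dermatological AEs, and application site reactions by visit.

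A reader might infer that the rules inflate TEAE rates materially, for example on the scale of the 0.7% to 1.8% reaction rates listed in Protocol 7. The documents do not support that. They give no frequency of pre-dose AEs, of intensity changes or of missing start dates. The Protocol 7 figures are also for single reaction terms, whereas the affected quantity is any TEAE from any cause.

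**What to change.** **SAP 5.6.** Define a TEAE as an AE that first starts on or after the first application, or that started earlier and later has an intensity higher than its last pre-dose intensity. State that successive intensity entries of one event are treated as one event, linked by an existing event identifier or by one assigned in programming.

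**SAP 6.1.** Add that an AE with a partial or missing start date is not treatment-emergent if its known stop date, or its stop month and year, is before the first application. Where the stop information does not settle the matter, keep the present default of counting the AE as treatment-emergent.

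The cost is about two sentences in the SAP, a linking step and a few lines of code, all of which can be done before unblinding. Neither new post-dose events nor worsened events are lost.

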| Evaluations:      | The number of facial inflammatory lesions (papules and pustules) will be recorded at baseline and each subsequent visit (Visits 2, 3 and 4). Erythema severity, the Investigator Global Assessment (IGA) and local irritation will be assessed at Baseline and all subsequent visits. The presence of Telangiectasia                                                                                                                                  |

[REDACTED]

|                   |                                                                                                                                                                                                                                                                                                                                                                                      |
|-------------------|--------------------------------------------------------------------------------------------------------------------------------------------------------------------------------------------------------------------------------------------------------------------------------------------------------------------------------------------------------------------------------------|
|                   | will be recorded at Baseline.                                                                                                                                                                                                                                                                                                                                                        |
| Endpoints: | 
The primary efficacy endpoint will be the mean percent change from baseline to Week 12 (Day 84) in the inflammatory (papules and pustules) lesion count.
 
The secondary endpoint will be the proportion of subjects with clinical success defined as a score of clear or almost clear (score of 0 or 1) on the Investigator Global Assessment (IGA) at Visit 4/Week 12.
 |
| Safety:    | The incidence of all adverse events reported during the study will be summarized by treatment group. Equivalence of the test and reference with regard to safety will be evaluated by comparing the nature, severity and frequency of their adverse event profiles.                                                                                                                  |

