**Protocol No: PRG-NY-15-013**

- a) [REDACTED] inflammatory lesions (papules and pustules) including those present on the nose.
  - b) At least moderate erythema, AND
  - c) Telangiectasia
4. Subjects may have [REDACTED] nodules (nodule defined as a papule or pustule greater than 5mm in diameter) at baseline.
  5. Subjects must have a baseline Investigator's Global Assessment (IGA) [REDACTED] on a severity scale of 0 to 4.
  6. Subjects must be willing and able to understand and comply with the requirements of the study, apply the medication as instructed, refrain from use of all other

- [REDACTED]
- [REDACTED]

during the 12 week treatment period, return for the required treatment period visits, comply with therapy prohibitions, and are able to complete the study.

7. Subjects must be willing to minimize controllable external factors that might trigger rosacea flare ups [REDACTED] throughout their participation in the study.
8. Subjects must be in general good health and free from any clinically significant disease, other than rosacea, that might interfere with the study evaluations.

9. [REDACTED]

[REDACTED]

[REDACTED]

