**5.9.2 Erythema Severity Assessment**

The severity of erythema is to be rated as follows:

| SCORE | ASSESSMENT | DESCRIPTION                         |
|-------|------------|-------------------------------------|
| 0     | None       | No redness present                  |
| 1     | Mild       | Slight pinkness to light red        |
| 2     | Moderate   | Definite redness, easily recognized |
| 3     | Severe     | Marked erythema; fiery red          |

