**5.10 Application Site Reaction Assessment**

At baseline (Visit 1/Day 1) and each subsequent visit, application site reactions such as dryness, burning/stinging, pruritus and scaling/peeling, are to be recorded.

[REDACTED]

[REDACTED]

[REDACTED]

The investigator will assess a subject's application site reaction by rating the following symptoms according to the scales provided below. Pruritus and stinging/burning symptoms will be assessed by discussion with the subject and will be reported as the severity experienced within 24 hours of the study visit.

**Dryness:** Mild Scaling, roughness, feeling of tightness, and possibly itching

| SCORE | ASSESSMENT | DESCRIPTION |
|-------|------------|-------------|
| 0     | None       |             |
| 1     | Mild       |             |
| 2     | Moderate   |             |
| 3     | Severe     |             |

**Scaling/Peeling:** Skin desquamation; shedding of the outer layers of the skin

| SCORE | ASSESSMENT | DESCRIPTION |
|-------|------------|-------------|
| 0     | None       |             |
| 1     | Mild       |             |
| 2     | Moderate   |             |
| 3     | Severe     |             |

**Pruritus:** Itching

| SCORE | ASSESSMENT | DESCRIPTION |
|-------|------------|-------------|
| 0     | None       |             |
| 1     | Mild       |             |
| 2     | Moderate   |             |
| 3     | Severe     |             |

**Stinging/Burning:** Stinging/tingling sensation

| SCORE | ASSESSMENT | DESCRIPTION |
|-------|------------|-------------|
| 0     | None       |             |

|   |          |            |
|---|----------|------------|
| 1 | Mild     | [REDACTED] |
| 2 | Moderate | [REDACTED] |
| 3 | Severe   | [REDACTED] |

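### SAP 5.6 summarizes erythema and application-site reaction scores only as by-visit distributions, which cannot show how many subjects worsened from their own baseline or were ever affected

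*SAP*

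**What the plan says.** The last-but-one paragraph of SAP 5.6 covers erythema severity, dryness, burning/stinging, pruritus and scaling/peeling in one sentence. It plans their frequency and distribution and ends "scaling/peeling will be summarized and compared descriptively by visit". The next line adds: "Safety comparisons will be performed only for the ITT population". Both are fully readable. Neither mentions change from baseline, a shift table, a worst post-baseline grade or a definition of worsening.

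The scores are paired with baseline:

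- The Protocol synopsis lists erythema among the assessments and says that "local irritation will be assessed at Baseline and all subsequent visits".
- Protocol 5.10 says: "At baseline (Visit 1/Day 1) and each subsequent visit, application site reactions such as dryness, burning/stinging, pruritus and scaling/peeling, are to be recorded". Each reaction is scored 0 to 3.
- Inclusion criterion 3b in Protocol 4.1 requires "At least moderate erythema, AND" telangiectasia. In Protocol 5.9.2 moderate is score 2 ("Definite redness, easily recognized") and severe is score 3, the top of the scale ("Marked erythema; fiery red").

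SAP 5.6 also has a separate adverse-event route. It plans a statistical evaluation of dermatological adverse events between Test and Reference, and it counts a subject once per preferred term at the highest severity.

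**The concern.** Comparing the safety profiles of Test and Reference is a stated objective (Protocol 2), and Protocol 7 names cutaneous irritation as the known reaction to the reference product. The scores are the structured, visit-by-visit record of local tolerability.

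A distribution at each visit discards the link to the subject's own baseline. It cannot distinguish an arm where nobody changed from one where as many worsened as improved. It also cannot distinguish the same few subjects reacting at every visit from different subjects reacting each time. Erythema adds a scale limit: a subject entering at grade 2 can rise by one grade only, and a subject entering at grade 3 cannot register worsening at all. Erythema is also a sign of the disease under treatment, so improvement pulls the whole distribution down while some subjects may get worse.

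**Working it through.** The documents give no figure for this point, and sample size and allocation are blacked out, so there is nothing to reproduce. From the documents come the 0-3 scales, the erythema entry range of 2 to 3, and the three post-baseline visits (Weeks 4, 8 and 12). **All rates below are assumptions.**

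**1. Share ever affected.** Suppose 5% have a new reaction at each of three visits.

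- Lowest share ever affected (same subjects each time): max(5, 5, 5) = 5%.
- Highest share (different subjects each time): 5 + 5 + 5 = 15%.

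The planned table reads 5%, 5%, 5% in both cases. Transient reactions are plausible, because Protocol 5.10 rates pruritus and stinging/burning over a 24-hour span only.

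**2. Share worsened, erythema.** Baseline is 80% grade 2 and 20% grade 3. At the visit, 40% are grade 1, 50% grade 2 and 10% grade 3. Two patterns give these same distributions (% of all subjects):

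| Move | Pattern A | Pattern B |
|---|---|---|
| 2 to 1 | 40 | 40 |
| 2 to 2 | 40 | 30 |
| 2 to 3 | 0 | 10 |
| 3 to 2 | 10 | 20 |
| 3 to 3 | 10 | 0 |
| Grade 2 at visit | 40 + 10 = 50 | 30 + 20 = 50 |
| Grade 3 at visit | 10 | 10 |
| Improved | 40 + 10 = 50 | 40 + 20 = 60 |
| Worsened | 0 | 10 |

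Worsening can only mean a move from 2 to 3, so it cannot exceed the 10% at grade 3. The distributions therefore allow 0% to 10% worsened. In pattern B that is 10/80 = 12.5% of the subjects able to worsen.

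**3. Active against vehicle.** Baseline is 20% severe. In the active arm 60% improve by one grade and 10% of moderate subjects worsen. In the vehicle arm 20% improve and nobody worsens.

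- Active: mild 0.8 × 0.6 = 48%; moderate 0.8 × 0.3 + 0.2 × 0.6 = 36%; severe 0.8 × 0.1 + 0.2 × 0.4 = 16%. The mean falls from 2.20 to 1.68, although 0.8 × 0.1 = 8% worsened.
- Vehicle: mild 0.8 × 0.2 = 16%; moderate 0.8 × 0.8 + 0.2 × 0.2 = 68%; severe 0.2 × 0.8 = 16%. The mean is 2.00.

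Percent severe is equal and the active arm looks better, although only that arm has worsening. With 10% severe at baseline, 9% of the active arm worsen and its mean still falls from 2.10 to 1.59. With 40% severe, 6% worsen and the mean falls from 2.40 to 1.86.

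**4. Test against Reference, equal improvement.** Both arms improve by 60%; only Test has 10% of moderate subjects worsening.

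- 20% severe at baseline: severe at the visit is 16% on Test and 0.2 × 0.4 = 8% on Reference.
- 10% severe at baseline: Test 0.9 × 0.1 + 0.1 × 0.4 = 13%; Reference 0.1 × 0.4 = 4%.

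Here the planned table does show the difference.

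**5. What full masking between two arms needs.** Take 100 subjects per arm, with dryness 50 at grade 0 and 50 at grade 1. In one arm nobody changes. In the other 20 go up and 20 go down: 50 - 20 + 20 = 50 at grade 0 and 50 + 20 - 20 = 50 at grade 1. The tables match at 0% against 20% worsened, but only because the second arm also has 20 improvements that the first lacks.

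**The case against.** The strongest reply is that the scores are a descriptive supplement. The Protocol synopsis and section 2.2 compare Test and Reference safety through adverse-event profiles, and SAP 5.6 tests dermatological adverse events. Counting a subject once at the highest severity already gives a per-subject summary across visits. Protocol 7.2 defines adverse events broadly enough to include new or worse irritation and asks for a separate entry when an event changes intensity. Section 7.3 requires reporting whether the event is observed, volunteered or elicited.

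Most of this stands, and it means the score table is not the only evidence on tolerability. It does not close the gap. No readable rule says that a higher score than at baseline becomes an adverse event. The SAP's treatment-emergent definition turns on occurrence after the first dose and does not mention worsening of a sign already present. Parts of Protocol 5.10, 7.3 and 8.1.5 are blacked out, so such a rule may exist there.

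Randomization is the second reply. A reader might infer that shared disease improvement would hide extra worsening on Test and so produce a false finding of similar tolerability. The documents do not support that: baseline scores and the erythema entry limit are alike in expectation across arms, and step 4 shows that extra worsening stays visible when improvement is equal.

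Third, no document supports the assumed rates. The only related figures, in Protocol 7, are adverse-reaction rates of 1.8%, 0.7% and 0.7%, which are not score rates. If most subjects start at 0 on a reaction, little improvement is available to offset worsening.

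**Conclusion.** The point holds as a limitation of the score summaries. By-visit distributions do not determine how many subjects worsened or were ever affected, and the fully readable SAP paragraph plans nothing else for these scores. In the assumed examples the unknown share is 0% to 10% for erythema worsening and 5% to 15% for subjects ever affected.

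Masking is strongest within an arm and against vehicle. For Test against Reference it needs offsetting improvement in the same arm, or reactions in different subjects at different visits.

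A reader might also infer that worsening counted this way is caused by the product. It need not be, because rater variation and natural fluctuation also move scores up and down. Severity is low: this is a descriptive safety display and the efficacy conclusions do not depend on it.

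**What to change.** In SAP 5.6, keep the by-visit table and add the following for erythema and each reaction, by arm, in the ITT population:

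- A shift table of baseline grade against worst post-baseline grade, showing also the number with no post-baseline score.
- The number and percent with an increase of at least 1 grade over baseline, with the Test minus Reference difference and its confidence interval (level and method stated).
- For erythema, percent worsened among subjects at baseline grade 2, with the number at grade 3 who cannot register worsening shown beside it.

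The cost is a few more tables from data already collected, with no protocol change. Taking the worst of several visits raises the counts through rater variation and natural fluctuation. The text should therefore say that they are read as between-arm differences and not as counts of product-caused reactions. The shift table does not remove the erythema ceiling; it only makes it visible.
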